3. PATIENT SELECTION

3.1 Target Population

Subjects will include men with multifocal, Gleason 7 or greater, clinically localized prostate cancer for whom the decision has been made to perform radical prostatectomy at Johns Hopkins Hospital. Subjects will be identified and recruited through the Outpatient Clinic of the Department of Urology and from the Multidisciplinary Prostate Cancer Clinic.

3.2 Inclusion Criteria

To be eligible for this study, patients must meet *all* of the following criteria:

- Histologically confirmed adenocarcinoma of the prostate (clinical stage T1c-T3b, N0, M0) without involvement of lymph nodes, bone, or visceral organs
- Initial prostate biopsy is available for central pathologic review, and is confirmed to show at least 2 positive cores and a Gleason sum of ≥7
- Radical prostatectomy has been scheduled at Johns Hopkins Hospital
- Age ≥18 years
- ECOG performance status 0-1, or Karnofsky score \geq 70% (see Appendix A)
- Adequate bone marrow, hepatic, and renal function:
 - WBC >3,000 cells/mm³
 - ANC >1,500 cells/mm³

IRB#: IRB0010377

Johns Hopkins University

- \circ Hemoglobin >9.0 g/dL
- Platelet count >100,000 cells/mm³
- Serum creatinine <1.5 × upper limit of normal (ULN)
- Serum bilirubin <1.5 × ULN
- \circ ALT <3 × ULN
- \circ AST <3 × ULN
- Alkaline phosphatase <3 × ULN
- The etiology of abnormal bilirubin and transaminase levels should be evaluated prior to study entry.
- Willingness to provide written informed consent and HIPAA authorization for the release of personal health information, and the ability to comply with the study requirements (*note*: HIPAA authorization will be included in the informed consent)
- Willingness to use barrier contraception from the time of first dose of MGA271 until the time of prostatectomy.

3.3 Exclusion Criteria

To be eligible for this study, patients should *not* meet *any* of the following criteria:

- Presence of known lymph node involvement or distant metastases
- Other histologic types of prostate cancers such as ductal, sarcomatous, lymphoma, small cell, and neuroendocrine tumors
- Prior radiation therapy, hormonal therapy, biologic therapy, or chemotherapy for prostate cancer
- Prior immunotherapy/vaccine therapy for prostate cancer
- Prior use of experimental agents for prostate cancer
- Concomitant treatment with other hormonal therapy or 5α-reductase inhibitors
- Current use of systemic corticosteroids or use of systemic corticosteroids within 4 weeks of enrollment (inhaled corticosteroids for asthma or COPD are permitted as are other non-systemic steroids such as topical corticosteroids)
- History or presence of autoimmune disease requiring systemic immunosuppression (including but not limited to: inflammatory bowel disease, systemic lupus erythematosus, vasculitis, rheumatoid arthritis, scleroderma, multiple sclerosis, hemolytic anemia, Sjögren syndrome, and sarcoidosis)
- History of malignancy within the last 3 years, with the exception of non-melanoma skin cancers and superficial bladder cancer
- Uncontrolled major active infectious, cardiovascular, pulmonary, hematologic, or psychiatric illnesses that would make the patient a poor study candidate
- Known prior or current history of HIV and/or hepatitis B/C

3.4 Inclusion of Minorities

Men of all races and ethnic groups will be considered for study participation. Candidates must conform to all eligibility criteria to be accepted into the study. Minority patients who meet entry criteria will be actively recruited, although the trial is not designed to measure differences in

outcomes between ethnic groups. The estimated breakdown of the target population by race and ethnicity is: 80% white/Caucasian, 15% black/African American, and 5% comprised of other ethnic minorities.

3.5 Prohibited Concomitant Medications

Concurrent use of other anticancer agents or therapies including other experimental treatments is not permitted. Patients may not currently be taking any other form of androgen deprivation therapy, antiandrogens, 5α -reductase inhibitors, chemotherapy, radiation therapy, biologic therapy, immunosuppressive medications, or systemic corticosteroids.

Within 30 days of administration of study drug, patients should not receive vaccines including but not limited to the live rotavirus vaccine, the live BCG (bacillus Calmette-Guerin) vaccine, the live influenza vaccine, the live measles vaccine, the live mumps vaccine, the live poliovirus vaccine, the live rubella vaccine, the smallpox vaccine, the typhoid vaccine, the varicella vaccine, and the yellow fever vaccine.

Because of the potential for unknown drug-drug interactions, concurrent use of all other agents, over-the-counter medications, herbal remedies, vitamins/minerals, and alternative therapies must be documented on the case report form (CRF).

4. REGISTRATION AND ENROLLMENT PLAN

4.1 Registration Procedure

Patients who are considered candidates for the study will first be evaluated for eligibility by one of the principal investigators, co-investigators, or the research nurse. After screening for eligibility, patients who are eligible to participate in the trial must be registered with the Sidney Kimmel Comprehensive Cancer Center (SKCCC) according to the instructions below. A record of patients who fail to meet entry criteria (*i.e.*, screen failures) will also be maintained. Registration must be completed before beginning any study-related activities.

To initiate registration at SKCCC, study personnel should forward copies of the signed informed consent form (with embedded research authorization/HIPAA form), the institutional registration form, plus any required pathology information/laboratory tests to the project manager by fax or email. Once eligibility is confirmed, each subject will be assigned a unique patient study identification number. Treatment must not commence until the patient has received his identification number.

Prior to protocol enrollment and initiation of treatment, subjects must sign and date an IRBapproved consent form. Authorized study personnel should fully explain the scope of the study to each patient before obtaining informed consent. Patients should be advised of any known risks inherent in the planned treatments/procedures, any alternative treatment options, their right to withdraw from the study at any time and for any reason, and their right to privacy. When obtaining informed consent, study personnel should: **first**, confirm that the patient has received and has had time to read the informed consent form (including the research authorization/HIPAA form); **next**, confirm eligibility as defined in Sections 3.2 and 3.3 (inclusion and exclusion criteria); and **finally**, obtain dated and signed informed consent. A copy of the signed informed consent should be supplied to the project manager.

To register a patient, the following documents must be completed and faxed [contact] or emailed ([contact]) to the study coordinator ([name]):

- signed patient consent form
- institutional registration form

• copies of the prostate cancer pathology report and baseline laboratory studies including CBC with differential, liver and kidney function tests. Other materials may also be sent if considered pertinent for confirming patient eligibility.

The principal investigator and/or other authorized study personnel will then review these documents to confirm eligibility. To complete the registration process, the project manager will assign a patient study number (*i.e.*, protocol patient number). This number is unique to the patient and must be written on all data and correspondence for the patient. The project manager will also register the patient with SKCCC's Clinical Research Office (CRO).

4.2 Expected Enrollment

A total of 32 patients will be included in this study. The first patients are expected to be enrolled in February 2016, once the protocol has been approved by the IRB. With an estimated enrollment rate of 3 patients per month, accrual is expected to be completed in 5-6 months.

4.3 Study Centers

This is a single-institution study that will be conducted only at Johns Hopkins through a collaboration between the Brady Urological Institute and the Sidney Kimmel Comprehensive Cancer Center.

4.4 Recruitment

Subjects will be recruited from the outpatient facilities of the Brady Urological Institute, and from the outpatient Multidisciplinary Prostate Cancer Clinic of the SKCCC. Patients will not receive payment or reimbursement for participation. Every effort will be made to include patients of racial and ethnic minorities who fulfill the eligibility criteria.

5. STUDY PLAN

[figure not shown]
5.1 Overview and Schema

This is a single-center, single arm, open-label pilot study evaluating the safety, anti-tumor effect, and immunogenicity of neoadjuvant MGA271 given prior to radical prostatectomy in men with high-risk localized prostate cancer. Patients will be recruited from the outpatient Urology clinic. Eligible patients will receive MGA271 at a dose of 15mg/kg IV given weekly for 6 doses beginning 50 days prior to radical prostatectomy. 14 days after the last dose of MGA271, prostate glands will be harvested at the time of radical prostatectomy, and prostate tissue will be examined for the secondary endpoints. Follow-up evaluation for adverse events will occur 30 days and 90 days after surgery. Patients will then be followed by their urologists according to standard institutional practices, but will require PSA evaluations every 3 (±1) months during year 1 and every 6 (±2) months during years 2-3.

Study Schema:

IRB#: IRB0010377

Johns Hopkins University

IRB#: IRB0010377

Johns Hopkins University

Table 1STUDY CALENDAR

Every effort should be made to keep visits, tests, and procedures on schedule. Acceptable deviations are listed below.

	Screening	Treatment	Radical	Follow-up, 30, and
	Evaluation ^a	Days (1, 8, 15,	Prostatectomy,	90 Days Post-op
		22, 29, 36)	Day 50 (+/- 3	(+/- 1 wk) ^{h,i}
		(+/- 1 day)	days)	
Informed consent	Х			
Medical history	Х		Х	
Review of medications	Х	Х	Х	X
Physical assessment	Х	Х	Х	
Vital signs	Х	Х	Х	
Height and weight	Х	Х	Х	
Performance status	X	X	Х	X
CT and bone scan ^b	(X)			
Hematology labs ^c	Х	Х	Х	X
Chemistry labs ^d	Х	Х	Х	X
Serum PSA ^e	X e		Х	Xe
MGA271 dose		Х		
Toxicity assessment	Х			X
Surgical specimen ^f			Х	
Pathologic review ^g	X		Х	
Sera for Immunoassays ¹	Х		Х	X
Whole Blood (100 mL) for PBLs collection		Xk		Xk
B7-H3 IHC	Xg		Xf	
Fc Receptor Genotyping		Xj		
TCR Repertoire (8.5 mL PaxGene DNA)		Xj	Xj	Xj
 a: The screening (pre-treatment b: Staging CT (if allergic to CT sc clinically indicated, and are no c: Hematology laboratories inclue eosinophil count), and platele 	an contrast, obtain ot mandatory. 1de hemoglobin, he	MRI with contrast) a matocrit, white blood	nd bone scans should o d cell count with differe	nly be performed if ntial (including absolute

eosinophil count), and platelets. In addition, prothrombin time (PT/INR) and activated partial thromboplastin time (APTT) should be checked as clinically indicated. These labs should be collected prior to treatment.

d: Chemistry laboratories include sodium, potassium, chloride, bicarbonate, urea nitrogen, creatinine, glucose, calcium, albumin, total protein, bilirubin, alanine aminotransferase (ALT), aspartate aminotransferase (AST), alkaline phosphatase, amylase, and lipase.

e: Serum PSA should be obtained pre-treatment (at least 30 days from biopsy) and on the day of surgery, and every 3 months (±1 mo) for post-op year one then every 6 months (±2 mo) for post-op years two and three.

f: Harvested prostate gland to be evaluated for tumor apoptosis, CD8⁺ T cell infiltration, as well as other secondary and exploratory endpoints.

g: Archival prostate core biopsies to be centrally reviewed at baseline prior to study entry; radical prostatectomy specimens to be processed at Johns Hopkins according to standard procedures. Archival tissue for B7-H3 IHC testing to be sent to MacroGenics.

h: The post-operative evaluations (30 and 90 days after prostatectomy) may take place over the telephone or in person, but patients are required to have hematology and chemistry labs collected at this time-point for safety purposes.
i: In addition, PSA should be measured every 3 months (±1 month) in the first year after prostatectomy, and every 6

months (±2 months) in the second and third years after prostatectomy.

- Fc Receptor Genotyping and TCR Repertoire is collected prior to treatment in one 8.5 mL PaxGene DNA collection j:
- tube. TCR Repertoire is collected on the day of surgery, and 30 and 90 days post-op. PBLs should be collected on treatment day 1 (pre-treatment), treatment day 36 (post-treatment), and follow-up day k: 30 (see Appendix F)
- See Appendix F for specimen collection instructions for Sera for immunoassays.

IRB#: IRB0010377

Johns Hopkins University

5.2 Screening/Pretreatment Evaluation

Before initiating any screening activities, the scope of the study should be explained to each patient. Patients should be advised of any known risks inherent in the planned procedures, any alternative treatment options, their right to withdraw from the study at any time and for any reason, and their right to privacy. After this explanation, patients should be asked to sign and date an IRB-approved informed consent form that meets the requirements of the Code of Federal Regulations (Federal Register Vol. 46, No. 17, January 27, 1981, part 50).

The pretreatment/screening visit will determine patient eligibility according to the inclusion and exclusion criteria. All subjects must undergo a number of baseline evaluations as part of this screening visit, as detailed below. All of these evaluations should be conducted within 21 ± 4 days of starting the protocol. This information is also summarized in the Study Calendar (Table 1).

- informed consent
- demographic information
- medical history, including review of systems
- performance status, using ECOG or Karnofsky scales (Appendix A)
- physical assessment
- vital signs: temperature, pulse, sitting blood pressure, respiratory rate
- height and weight
- current medication list, including drug allergies/adverse events
- hematological laboratories (hemoglobin, hematocrit, white blood cell count with differential [including absolute eosinophil count], platelets); coagulation profile (INR, aPTT) if clinically indicated
- serum chemistry profile (sodium, potassium, chloride, bicarbonate, urea, creatinine, glucose, calcium, albumin, total protein, bilirubin, ALT, AST, alkaline phosphatase, amylase, lipase)
- serum PSA level
- CT (If allergic to CT scan contrast, obtain MRI with contrast) and/or bone scan, only if clinically indicated (not mandatory)
- central pathologic review of prostate core biopsies
- Sera for immunoassays

After all relevant screening information is documented, registration should be finalized and appropriate documents (*i.e.*, signed informed consent, supporting source documentation for eligibility) should be faxed or emailed to the program manager.

Information on patients who do not meet eligibility criteria to participate in this study (*i.e.*, screening failures) should also be captured at the pretreatment visit.

5.3 Treatment Visits

Treatment initiation with MGA271 may begin at least 1 week after diagnostic biopsy granted the patient does not have any complications from biopsy. The following must be performed on treatment days (days 1, 8, 15, 22, 29, 36) (±1 day) with administration of MGA271.

- performance status
- review of medication list

IRB#: IRB0010377

Johns Hopkins University

- review of toxicity/adverse events
- height/weight
- vital signs (before, halfway through, and after 2-hr infusion)
- physical exam (focused)
- hematological laboratories and serum chemistry profile
- PBMC collection for TCR repertoire
- Whole blood for PBLs (treatment days 1 and 36 only)
- Whole blood for Fc receptor genotyping Day 1 only
- Administration of MGA271 15mg/kg IV (see section 6.3 Study Drug Administration)

5.4 Radical Prostatectomy

The following must be performed on the day of radical prostatectomy, which itself should occur 50 (± 3) days after the administration of the first dose of MGA271.

- medical history
- performance status
- physical assessment, including vital signs
- review of medication list
- review of toxicity/adverse events
- hematological laboratories and serum chemistry profile
- serum PSA
- collection of prostatectomy tissue for analysis of study endpoints
- pathological processing of prostatectomy specimen according to standard procedures
- Sera for immunoassays
- PBMC collection for TCR Repertoire

5.5 Follow-Up Evaluations

Follow-up visit scheduled for 30 days and 90 days after radical prostatectomy may occur in the outpatient clinic. Required evaluations during this follow-up visits are listed below. Patients should then continue to be followed by their treating urologist according to standard institutional practices.

- performance status
- review of medication list
- review of toxicity/adverse events
- hematological laboratories and serum chemistry profile
- Serum PSA at post-operative day 90
- Sera for immunoassays
- PBMC collection for TCR Repertoire
- Whole blood for PBLs (post-op day 30 only)

Patients withdrawing from the study early because of adverse events should be followed until the adverse event has either resolved or stabilized. Reasons for premature withdrawal should be determined and documented.

In addition, patients will be required to have a structured assessment of post-operative PSA measurements for 3 years. In the first year after prostatectomy, PSA will be measured every 3 months (±1 mo). In the second and third years after prostatectomy, PSA will be measured every 6 months (±2 mo). These PSA measurements may be obtained outside of Johns Hopkins, but the results need to be made available to the study team.

5.6 Duration of Therapy

Participation in this study will be terminated for any of the following reasons listed below:

- the patient decides to withdraw from the study (withdrawal of consent) due to unacceptable toxicities or for any other reason
- the patient completes all of the protocol procedures and follow-up requirements
- there are adverse events that, in the judgment of the investigator, may cause severe or permanent injury or are incompatible with continuation on study
- there are major violations to the study protocol or the patient is noncompliant with treatments, as judged by the investigator
- the patient experiences concurrent illness or a change in his condition that, in the judgment of the investigator, renders him unacceptable for further treatment on study
- the patient dies
- the patient is lost to follow-up
- the study is prematurely terminated for safety or feasibility concerns or other reasons

Patients should be removed from the study when any of the above criteria are met. Because an excessive rate of withdrawals can render the study uninterpretable, unnecessary withdrawal of patients should be avoided if possible. When a patient leaves the study early, the investigator should make every effort to contact the patient and to perform the final follow-up evaluation (even by telephone interview). The reason for removal of a patient from the study, and the date of removal, must be appropriately documented.

Patients will be replaced if they are removed from the study after signing the informed consent but before undergoing radical prostatectomy. Patients receiving at least one dose of the study drug will be included in safety analyses, and those also undergoing prostatectomy will be used for the efficacy analyses.

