6.4.5.2 Grade 3 or 4 AEs

Drug administration should be held upon observation of AEs of \geq Grade 3 severity to enable patient management, monitoring of the resolution of the event, and assessment of the relatedness of the event. An AE of \geq Grade 3 that is considered related to MGA271 will result in discontinuation of therapy unless otherwise specified in the protocol. For AEs associated with liver function test abnormalities, drug administration should also be discontinued for concomitant ALT >3xULN and total bilirubin >2x ULN without an alternative etiology (Hy's Law).

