8.2 Primary Endpoint

8.2.1 Rate of adverse events

All subjects receiving at least one dose of the study drug will be evaluated for safety by monitoring symptoms, physical examinations, and laboratory tests. Adverse events will be classified and graded according to the NCI Common Toxicity Criteria version 4.0 (see Appendix B). The absolute number and frequency of each adverse event will be reported, and subdivided according to toxicity grade. A description of adverse events by treatment arm will also be reported. A particular adverse event occurring more than once in the same subject will be counted only once and at its worse grade.

- 8.2.2 In expansion cohort (amendment 1):
 - All subjects receiving at least one dose of the study drug will be assessed for PSA₀ Response Rate (Undetectable PSA level <0.1 ng/mL) at 12 months following radical prostatectomy

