10.3 Analysis Populations

10.3.1 Intention-to-treat population

All patients who meet eligibility criteria and receive at least one dose of the study drug will be included in the analysis of the primary and secondary endpoints, even if there are subsequent protocol deviations. However, in cases where prostatectomy is not performed or if adequate surgical tissue is not collected, then determination of the secondary endpoints (apoptosis/proliferation marker analysis, tissue CD8⁺ T cell analysis) will not be possible. Patients will be replaced if they are removed from the study after signing the informed consent but before receiving the study drug.

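### Section 5.6 ends study participation on treatment-related grounds and requires no PSA afterwards, while 8.2.2, 10.1 and 10.3.1 count every dosed man in the 12-month PSA₀ analysis

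*Combined protocol and SAP*

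**What the plan says.** Section 5.6 lists reasons for ending participation in the study, then states: "Patients should be removed from the study when any of the above criteria are met". Several of the reasons concern treatment:

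- Non-compliance or violations: "there are major violations to the study protocol or the patient is noncompliant with treatments, as judged by the investigator".
- Adverse events that, in the investigator's judgment, "may cause severe or permanent injury or are incompatible with continuation on study".
- Illness or a change in condition that, in the investigator's judgment, "renders him unacceptable for further treatment on study".

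Three provisions cover a man who leaves early. Section 5.5 follows a man who withdraws because of an adverse event until it resolves or stabilises. Section 5.6 asks for a final evaluation, which may be by telephone. Section 11.5 provides safety assessments. None of them mentions PSA.

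On the analysis side, 8.2.2 states: "All subjects receiving at least one dose of the study drug will be assessed for PSA"₀ response at 12 months after prostatectomy. Section 10.1 puts men with at least one dose in both the safety and the efficacy analyses. Section 10.3.1 says that eligible men with at least one dose "will be included in the analysis of the primary and secondary endpoints, even if there are subsequent protocol deviations".

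The end of 5.6 differs. It uses for efficacy only dosed men who also had prostatectomy, and it replaces men removed between consent and surgery. Section 10.1 repeats that replacement rule. Section 10.3.1 replaces only men removed before receiving study drug.

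**The concern.** Dosing takes about five weeks and the endpoint falls a year after surgery, so stopping the drug is no statistical reason to stop measuring PSA. A site that applies 5.6 as written may close the PSA schedule for men whom the analysis sections say must be counted. Major violations show the clash most plainly: they are a ground for removal in 5.6, while 10.3.1 keeps men with protocol deviations in the analysis.

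At stake is what the PSA₀ rate describes. It is a primary endpoint of the expansion, meant to inform the design of larger trials. If removed men have no 12-month PSA, or are replaced, the rate describes men who tolerated and complied with six doses rather than all men treated. Time to PSA recurrence is affected in the same way, because a removed man is censored at his last recurrence-free PSA. No rule says how a missing 12-month PSA is counted.

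**Working it through.** **1. The plan's own figure.** Section 10.2.1.1 gives 90% intervals for 0 to 3 responders among 32 men. The two-sided Wilson score interval is

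[p + z²/(2n) ± z·√(p(1−p)/n + z²/(4n²))] / (1 + z²/n), with z = 1.645 and n = 32.

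For 0 responders the upper limit reduces to z²/(n + z²) = 2.706/34.706 = 7.8%. The other rows come out as 0.7–12.9%, 2.1–17.2% and 3.8–21.3%. All four match the plan; exact Clopper-Pearson limits do not (0 responders: upper limit 8.9%). The table therefore assumes 32 known outcomes and none missing.

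**2. When removal happens.** Doses fall on days 1 to 36 and surgery on day 50 ± 3 (5.1, Table 1). A removal tied to treatment will normally come before surgery. The passages then give different denominators for m such men:

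| Rule followed | Dosed | With a required 12-month PSA |
|---|---|---|
| 10.3.1 (no replacement after dosing) | 32 | 32 − m |
| 5.6 and 10.1 (replace before surgery) | 32 + m | 32 |

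Under 5.6 the m men also leave the efficacy set unless they had surgery. Under 10.1 they are replaced but stay in it.

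**3. Effect of each missing outcome.** With n = 32, the distance between counting all missing men as failures and all as responders is m/32:

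| m | 1 | 2 | 4 | 6 | 8 |
|---|---|---|---|---|---|
| Range (points) | 3.1 | 6.2 | 12.5 | 18.8 | 25.0 |

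With replacement it is m/(32 + m), for example 4/36 = 11.1 points.

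**4. How many men.** The documents give no removal rate. Two figures serve as assumed proxies:

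- One of 51 men stopped for drug-related toxicity (2.3.2): 32 × 1/51 = 0.6 men, a range of about 2 points.
- 18 of 160 had serious or severe related effects (2.2.3.2): 32 × 18/160 = 3.6 men, a range of about 11 points.

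The second counts events, not discontinuations. Neither counts removals for non-compliance, violations or unrelated illness.

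**5. Illustration with m = 4 (responder counts assumed).**

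- No replacement, 18 responders among 28 followed: complete cases 64.3% (90% CI 48.7–77.3); missing as failures 18/32 = 56.2% (41.9–69.6); missing as responders 22/32 = 68.8% (54.3–80.3).
- With replacement, 20 responders among 32 followed of 36 dosed: 62.5% in those followed (48.0–75.1), against 20/36 = 55.6% and 24/36 = 66.7% among all dosed.

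**6. Direction.** Without replacement, the complete-case error is (m/32) × (rate in followed men − rate in removed men). Take m = 4, an assumed 60–75% in followed men and 30–50% in removed men. The error then runs from 0.125 × (0.60 − 0.50) = 1.2 points to 0.125 × (0.75 − 0.30) = 5.6 points upward. If removed men did as well as the others it would be zero, and if they did better it would change sign.

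**The case against.** A reader might infer that every man who must stop the drug is automatically removed and his PSA lost. The documents do not say that. The drug-stopping rules in 6.4.4 and 6.4.5 end drug only; a related event of Grade 3 or above "will result in discontinuation of therapy unless otherwise specified in the protocol", with nothing said about study status. The removal criteria for adverse events, non-compliance and illness rest on the investigator's judgment, and 5.6 asks that unnecessary withdrawals be avoided. Section 5.5 sets out the three-year PSA schedule straight after the paragraph on early withdrawal, does not tie it to completing treatment, and accepts outside results. A site could reasonably go on collecting PSA. All of this stands, so the point is that PSA is not required after removal, not that it is certain to be lost.

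A reader might also infer that the rate is biased upward. Nothing in the documents links toxicity or partial dosing to post-operative PSA, so informative missingness is plausible but not shown. The reported discontinuation figure, 1 of 51, suggests that the number could be small.

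Nor is it settled that every dosed man must be analysed, because the end of 5.6 says otherwise. That sentence does not close the gap. A man removed from the study who still has his prostatectomy remains in the efficacy set under 5.6, with no PSA required.

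**Conclusion.** The inconsistency holds. Section 5.6 ties leaving the study to treatment-related grounds, defines no status for a man off drug but still followed, and requires no PSA after removal. Sections 8.2.2, 10.1 and 10.3.1 need his 12-month outcome. The efficacy-population and replacement sentences of 5.6, 10.1 and 10.3.1 also disagree with each other, so the PSA₀ denominator is not fixed. Followed literally, 5.6 allows an estimate confined to men who tolerated and complied with the regimen.

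The size is about 3.1 points of worst-to-best-case range for each missing man out of 32. Under the two assumed proxies the total is about 2 to 11 points. The size and direction of any actual bias cannot be derived from the documents. This should be corrected, because a PSA that was never collected cannot be recovered at analysis.

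**What to change.** 1. In 5.6, separate discontinuation of study drug from withdrawal from the study. Leave the drug-stopping criteria unchanged.
2. State that a dosed man stays in follow-up for surgical outcomes, adverse events and PSA on the existing schedule, unless he withdraws consent for follow-up, dies or is lost. Outside PSA results count, as 5.5 already allows.
3. Reconcile the efficacy-population and replacement sentences of 5.6, 10.1 and 10.3.1 so that one denominator applies.
4. Report the PSA₀ rate among all dosed men, with a missing 12-month PSA counted as non-response, and give best- and worst-case bounds beside it. Say explicitly that this covers a dosed man who never has surgery and so has no 12-month date.

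The cost is a short amendment and the retrieval of a few extra PSA results. The reported rate may be slightly lower, because missing outcomes count against it.
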